6.10. Continued Access Period

The continued access period begins after study completion and ends at end of trial (Figure JVDF.2 and Section 4.4).

Attachment 1 presents the schedule of events, including AE/serious adverse event (SAE) data collection and a continued access follow-up visit, to occur 30 days after discontinuation from the

continued access period or when the patient starts a new anticancer therapy, whichever happens first.

Patients receiving IPs and experiencing ongoing clinical benefit, without disease progression, and no undue risks may continue to receive IP after study completion in the continued access period until one of the criteria for discontinuation is met, including unacceptable toxicity or pregnancy (Section 7.1). Patients may receive a maximum of 35 cycles (approximately 2 years) of study treatment.

Lilly will notify investigators when the continued access period begins and ends.

7. Discontinuation Criteria

The reason for discontinuation and the date of discontinuation will be collected for all patients. All enrolled patients who discontinue, regardless of whether or not they received IPs, will have procedures performed as shown in the Time and Events Table ([Attachment 1](#)).

If a patient withdraws informed consent, he or she must not be contacted unless he or she has explicitly provided permission and consent. Lilly may continue to use previously collected medical research data prior to the withdrawal consistent with the original authorization.

7.1. Discontinuation from Study Treatment

Patients are considered to have discontinued from study treatment when BOTH pembrolizumab and ramucirumab will no longer be administered.

Details regarding discontinuation due to an AE or due to pregnancy are found in Section [6.6](#), Section [8.2.1](#), and Section [8.2.1.2](#)). Patients will be discontinued from study treatment if they meet any of the following additional criteria:

- enrollment in any other clinical trial involving an IP or enrollment in any other type of medical research judged not to be scientifically or medically compatible with this study
- The patient, for any reason, requires treatment with another therapeutic agent that has been demonstrated to be effective for treatment of the study indication, discontinuation from the study occurs prior to introduction of the new agent.
- The investigator decides that the patient should be discontinued from study treatment.
- The patient requests that the patient be withdrawn from study treatment.
- The patient is significantly noncompliant with study procedures and/or treatment.
- disease progression (must be confirmed if patient is clinically stable [[Section 8.1.1.3](#)])
- Discontinuation of treatment may be considered for patients who have attained a confirmed CR that have been treated for at least 24 weeks and had at least 2 cycles of study treatments beyond the date when the initial CR was declared.

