4.1.3. Study Period and Continued Access Definitions

Terms used to describe the periods during the study are defined below and illustrated in [Figure JVDF.2](#).

- **Baseline/Screening:** begins when the informed consent form (ICF) is signed, and ends at the first study treatment (defined as receiving either ramucirumab or pembrolizumab); if no study treatment is given, baseline/screening ends at discontinuation. Lasts up to 28 days.
- **Study Period:** begins at the time of first study treatment and ends at study completion, which occurs approximately 2 years after the first patient received first study treatment (Section 4.4).
 - **Study Treatment Period:** begins with the day of the first patient's first study treatment and ends the day that the decision is made to discontinue study treatment (discontinuation of both study drugs; Section 7.1). Individual patients who enroll in Study JVDF may continue treatment for up to 35 cycles (approximately 2 years), until they have confirmed progressive disease or discontinued study treatment for any other reason.
 - **Postdiscontinuation Follow-Up** consists of the following 2 phases.
 - **Short-Term (Safety) Follow-Up:** begins the day after the patient and the investigator agree that the patient will discontinue study treatment and ends with the short-term follow up visit, to occur approximately 30 days thereafter.
 - **Long-Term (Survival) Follow-Up:** begins the day after short-term follow-up is completed and ends with the patient's death, loss to

follow-up, or overall study completion, whichever is earlier. The long-term follow-up visit will occur approximately 90 days after the decision is made to discontinue from study treatment. Subsequent follow-up (not a formal visit) will occur approximately every 90 days thereafter, for up to approximately 2 years from the first study treatment (Attachment 1).

- **Continued Access Period:** begins after study completion (final analysis and evaluation of the study endpoints) and ends at end of trial (defined in Section 4.4). In the continued access period, individual patients may continue the current study treatment after study completion, as long as they experience ongoing clinical benefit (details in Section 6.10). Sites will be notified when the continued access period is to begin and end.

Patients who are in short-term follow-up when the continued access period begins will complete the 30-day short-term follow-up visit and then discontinue the study.

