7.2. Discontinuation from the Study

Patients will be discontinued from the study in the following circumstances:

- The investigator decides that the patient should be discontinued from the study.
- The patient requests that the patient be withdrawn from the study.

- The patient becomes pregnant during the study. See Section 8.2.1.3 regarding reporting requirements on fetal outcome and breastfeeding.
- Lilly stops the study or stops the patient's participation in the study for medical, safety, regulatory, or other reasons consistent with applicable laws, regulations, and good clinical practice (GCP).

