9.3.1.1. Postdiscontinuation Therapy

The numbers and percentages of patients reporting postdiscontinuation therapies will be provided overall, by type of therapy (surgery, radiotherapy, or systemic therapy), and by drug name.

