Tumor imaging and assessment		X		X	X	X	Assessments previously obtained as part of routine clinical care may be used as the baseline assessment if performed within 21 days prior to enrollment. Imaging is not required on Cycle 1 Day 1. SEE FOOTNOTE.
Survival information					X	X	Follow-up for the collection of survival data and subsequent anticancer treatments should be attempted at regularly scheduled intervals (every 90 days [±7 days]) for up to 2 years after patients receive the first dose. This follow-up might be a phone call to the patient, her/his family, or local doctor.
Additional Analyses							
Tumor tissue	X						New biopsy at baseline (recent to Cycle 1 Day 1) is required. For first line NSCLC, PD-L1 >=1% is required. Tumor tissue collection during the treatment period is optional, and can be provided if available, for example in case of a clinically-indicated biopsy.
Genetics Whole Blood Sample			X				Collect 1 sample prior to treatment on Cycle 1 Day 1.
• Biomarker • Pharmacokinetics • Immunogenicity	See Attachment 2 .						

	Study Period						Notes	
	Baseline (within 28 days prior to enrollment)			Treatment (21-day cycles)		Postdiscontinuation Follow-Up		
Procedure	≤28 days	≤21 days	≤7 days	Day 1	Day 8	Short-Term Follow-Up Visit (30 ±7 days)	Long-Term Follow-Up Visit (every 90 ±7 days)	The first study treatment will be administered within 7 days following enrollment. Postdiscontinuation follow-up begins when the decision is made that the patient will no longer continue study treatment.
Administration of Study Drugs								Day 8 procedures are only for Cohort A, A1, and A2 (Gastric-GEJ or BTC Ram 8 mg/kg, Days 1 and 8). Long-term follow-up should be attempted at regularly scheduled intervals (every 90 days [±7 days]) until death, loss to follow-up, or study completion (whichever occurs first).
Administer Ramucirumab								Administer ramucirumab first per the dose schedule to which the patient is allocated. For first 2 cycles, implement a 1-hr observation period i) between ramucirumab and pembrolizumab administration, and ii) after pembrolizumab infusion. For all cycles thereafter, no observation period will be required unless clinically indicated.
BTC 8 mg/kg				X	X			
Gastric-GEJ 8 mg/kg				X	X			
Gastric-GEJ 10 mg/kg				X				
NSCLC 10 mg/kg				X				
Urothelial 10 mg/kg				X				
Administer Pembrolizumab								
200 mg fixed				X				

Time and Events Table (concluded)

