Attachment 7. Protocol JVDF Restricted and Prohibited Concomitant Therapy

The table below describes medications, treatments, and drug classes restricted or prohibited, with exceptions and conditions for use during the study treatment period (there are no prohibited therapies during the follow- up period). Patients who, in the assessment by the investigator, require the use of any of the prohibited treatments for clinical management should be removed from the trial. Patients may receive other supportive therapy or vaccinations that the investigator deems to be medically necessary.

Generally, medications or live vaccinations specifically prohibited in the exclusion criteria are not allowed during the ongoing trial.

Therapy	As Needed	Chronic Use	Exceptions or Conditions for Use
Anti-platelet therapy	yes	no	Chronic use of aspirin up to 325 mg/day is permitted.
Anticoagulation therapy	no	Yes, with restrictions	At enrollment, patients on full-dose anticoagulation must be on a stable dose (minimum duration 14 days) of oral anticoagulant or low molecular weight heparin or similar agent. If on warfarin, the patient must have an INR ≤ 3 and no active bleeding or pathological condition present that carries a high risk of bleeding (e.g., tumor involving major vessels or known varices).
Anti-cancer biological therapy	no	no	
Chemotherapy	no	no	
Colony-stimulating factors	yes	no	Follow local guidelines.
Erythroid growth factors	yes	no	Follow local guidelines.
Experimental medicines or investigational agents	no	no	Other than ramucirumab or pembrolizumab
Glucocorticoids	no	no	Systemic glucocorticoids are permitted to modulate symptoms from an event of suspected immunologic etiology. The use of physiologic doses of corticosteroids may be approved after consultation with the Sponsor. Note: Inhaled steroids are allowed for management of asthma.
Immunotherapy (including vaccinations)	no	no	Other than pembrolizumab OR inhaled steroids Live vaccines are NOT allowed within 30 days prior to the first study treatment and while participating in the trial. Examples of live vaccines include, but are not limited to, the following: measles, mumps, rubella, chicken pox, yellow fever, rabies, BCG, and typhoid (oral) vaccine. Seasonal influenza vaccines for injection are generally killed virus vaccines and are allowed. However, intranasal influenza vaccines (e.g., Flu - Mist®) are live attenuated vaccines, and are not allowed.

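### Protocol 7.1 and Attachment 7 take a patient who needs another agent off the study, while the rest of the protocol keeps that patient in survival follow-up; OS data are at risk if sites apply the literal wording

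*Protocol*

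**What the plan says.** Section 7.1 of the protocol concerns stopping study treatment, which it defines as both drugs no longer being given. Its list opens with "Patients will be discontinued from study treatment if they meet any of the following additional criteria". One bullet covers a patient who, for any reason, needs another agent shown to be effective for the indication. It ends: "discontinuation from the study occurs prior to introduction of the new agent".

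Attachment 7 lists restricted and prohibited therapies, including chemotherapy and anticancer biologics. It says that patients who, in the investigator's assessment, "require the use of any of the prohibited treatments for clinical management should be removed from the trial". Its scope is the study treatment period, and it adds that "there are no prohibited therapies during the follow- up period".

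Other parts of the protocol describe continued follow-up:

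- The introduction to Section 7 sends every enrolled patient who discontinues to the Time and Events Table. It bars contact only where consent is withdrawn.
- Section 7.2 opens with "Patients will be discontinued from the study in the following circumstances" and lists investigator decision, patient request, pregnancy and a sponsor stop. New anticancer therapy is not listed.
- In Section 4.1.3, survival follow-up "begins the day after short-term follow-up is completed and ends with the patient's death", loss to follow-up or study completion, whichever is earlier.
- Attachment 1, in the survival row, says: "Follow-up for the collection of survival data and subsequent anticancer treatments should be attempted at regularly scheduled intervals".
- Section 9.3.1.1 states: "The numbers and percentages of patients reporting postdiscontinuation therapies will be provided overall". SAP 5.3.5 repeats this plan.

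For OS, protocol Section 8.1.3 censors at the last date known alive, and SAP 5.2.1.4 at the last contact before the data cut-off.

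**The concern.** The protocol separates leaving study treatment from leaving the study, and other bullets in the same 7.1 list use the treatment term. A site therefore has reason to read this bullet literally. A site that does so closes the patient before the next agent starts; a site working from Attachment 1 keeps calling every 90 days.

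OS is a secondary endpoint, estimated by Kaplan-Meier in each cohort. If contact stops before the new agent, the last date known alive falls at about that date, and the existing censoring rule then censors OS there. Needing another agent is related to prognosis, so this censoring is not independent of survival. Site differences in reading would also make follow-up uneven across cohorts of 15 or 25 patients.

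The same loss would affect the post-discontinuation therapy summaries. It would also affect the SAP 5.3.8 summary of deaths more than 30 days after the last infusion; deaths are among the safety endpoints of the primary objective.

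**Working it through.** The documents give no OS sample size, event target or stated figure to reproduce. The main check is therefore of the text; the arithmetic only illustrates possible size.

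**Step 1. Passages side by side**

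| Place | What happens to a patient who needs another agent |
|---|---|
| Protocol 7.1, lead-in | Leaves study treatment |
| Protocol 7.1, bullet | Leaves the study before the agent starts |
| Attachment 7 | Leaves the trial (treatment period only) |
| Section 7 introduction | Follows the Time and Events Table |
| Section 7.2 | Not a listed reason for leaving the study |
| Section 4.1.3 and Attachment 1 | Followed to death, loss to follow-up or study completion; later anticancer therapy recorded |
| Section 8.2.1.1.3 | Pembrolizumab events of clinical interest collected up to 30 days after a new therapy starts, within a 90-day limit |
| Protocol 9.3.1.1 and SAP 5.3.5 | Later therapies summarised |

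The 7.1 bullet and the Attachment 7 sentence cannot both be applied literally and leave the other rows workable.

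**Step 2. Who is exposed**

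Progression has its own bullet in 7.1. A patient who stops for progression is in follow-up before the next line starts, and Attachment 7 prohibits nothing there. Those exposed are therefore mainly patients who need another agent while still on study drug. Patients already off drug are included only on a broad reading of the 7.1 bullet's *for any reason*. Neither document gives the size of either group.

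**Step 3. Upper-end illustration**

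Anchor: ramucirumab alone in gastric-GEJ cancer (protocol Table JVDF.1), median PFS 2.1 months and median OS 5.2 months. Assumptions, none from the documents:

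- time to progression is exponential with rate ln 2 / 2.1 per month;
- survival after progression is exponential, scaled so that true median OS is 5.2 months;
- a share f starts a new agent at progression and is censored there;
- their post-progression hazard relative to the others (HR) is 1 or 0.5;
- every patient is cut off at 24 months.

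Share of deaths missed = f × P(a patient starting a new agent dies by 24 months) / P(any patient dies by 24 months). Both probabilities are near 1, so the share is close to f. Results from 200,000 simulated patients:

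| f | HR | Deaths missed | KM median, months (true 5.2) | 12-month OS, true → KM |
|---|---|---|---|---|
| 20% | 1 | 20% | 5.59 | 10.0% → 11.9% |
| 20% | 0.5 | 20% | 5.27 | 11.0% → 9.9% |
| 40% | 1 | 40% | 6.21 | 10.1% → 15.1% |
| 40% | 0.5 | 40% | 5.55 | 11.6% → 11.7% |
| 60% | 1 | 60% | 7.24 | 10.1% → 21.0% |
| 60% | 0.5 | 60% | 6.35 | 11.4% → 17.0% |

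A second set of assumptions used median time to progression 3 months, a new agent one month later in 30% to 70% of patients, and later median survival of 5 to 8 months with the agent and 2 to 5 without. Observed deaths per 25 patients fell from about 21–24 to about 7–17, and 12-month OS shifted by −5 to +19 percentage points. In both sets the 12-month shift takes either sign, depending on the assumed prognosis of those who start another agent.

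**Step 4. Scaling to the narrower group**

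In the second set, a 50% share loses about 11 deaths per 25 patients. Scaling in proportion, an assumed 5% share loses 11 × 5/50 = 1.1 and an assumed 10% share loses 11 × 10/50 = 2.2, or about one to two deaths per cohort.

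**The case against.** The strongest reply is that the intended design is clear and one bullet is misworded. The Section 7 introduction governs both 7.1 and 7.2 and sends all discontinuing patients to a table that includes survival and later therapies. The 7.1 lead-in, the 7.2 list and Section 4.1.3 agree with it. This stands as evidence of intent, but it does not remove the contrary instructions: a site still holds two that it cannot both follow.

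A reader might infer that the plan censors OS at next-line therapy. The documents do not support that. The protocol censors at the last date known alive and the SAP at last contact; neither names new therapy. The effect arises only through sites ending contact.

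A reader might also apply the larger simulated losses to all next-line patients. That is not supported either. Most such patients would be off drug for progression and outside Attachment 7. The simulations also give every patient 24 months, whereas the final analysis falls about two years after a first patient's first treatment (by cohort group in SAP 5.3.15), so later enrollees have less follow-up.

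Nor can a loss of day-90 SAE data be put down to the 7.1 wording alone. Section 8.2.1.2 already ends SAE collection 30 days after treatment stops if new anticancer therapy begins.

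Finally, OS here is descriptive, single-arm and secondary. That stands and limits the weight of the point.

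**Conclusion.** The contradiction is in the current text and needs no assumption. The 7.1 bullet and the Attachment 7 sentence conflict with the lead-in to 7.1 itself, the Section 7 introduction, Section 7.2, Section 4.1.3, Attachment 1 and the planned therapy summaries.

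The consequence for OS is conditional on sites acting on the literal wording. It would then be informative censoring at about the start of the new agent, possibly uneven between sites, and not reliably correctable because the survival data would not have been collected. Its size is unknown. About one to two deaths per 25-patient cohort follows from an assumed 5% to 10% exposed share, and the 20% to 60% losses are upper-end illustrations. No direction of bias is established. The response-rate power tables are unaffected. This should be corrected, but it does not threaten the design.

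**What to change.** - In the 7.1 bullet, change *discontinuation from the study* to *discontinuation from study treatment*, and add that the patient continues in short-term and long-term follow-up.
- In Attachment 7, change *removed from the trial* to *discontinued from study treatment and followed per Attachment 1*.
- Leave the rule on when study treatment stops as it is.
- Separately, reconcile the SAE window. Section 8.2.1.2 shortens collection when new anticancer therapy starts, whereas Table JVDF.7 and Attachment 1 call for all SAEs through the 90-day visit without that exception. The 7.1 edit does not settle this.

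The cost is two wording changes in the next amendment, a site memo, and a decision on the SAE window. The follow-up edits add no visits, because Attachment 1 already schedules the contacts. They add no scans, because Section 8.1.1.2 already ends imaging at new anticancer treatment.

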7.1.1. Discontinuation of Inadvertently Enrolled Patients

The criteria for enrollment must be followed explicitly. If the Sponsor or investigator identifies a patient who did not meet enrollment criteria and was inadvertently enrolled, a discussion must occur between the Sponsor CRP and the investigator to determine if the patient may continue in the study. If both agree it is medically appropriate to continue, the investigator must obtain documented approval from the Sponsor CRP to allow the inadvertently enrolled patient to continue in the study with or without treatment with study drug(s).

7.2. Discontinuation from the Study

Patients will be discontinued from the study in the following circumstances:

- The investigator decides that the patient should be discontinued from the study.
- The patient requests that the patient be withdrawn from the study.

- The patient becomes pregnant during the study. See Section 8.2.1.3 regarding reporting requirements on fetal outcome and breastfeeding.
- Lilly stops the study or stops the patient's participation in the study for medical, safety, regulatory, or other reasons consistent with applicable laws, regulations, and good clinical practice (GCP).

7.2.1. Patients Who are Lost to Follow-Up

A patient will be considered lost to follow up if he or she repeatedly fails to return for scheduled visits and is unable to be contacted by the study site. Site personnel are expected to make diligent attempts to contact patients who fail to return for a scheduled visit or who the site is otherwise unable to follow.

8. Study Assessments and Procedures

Written informed consent must be obtained prior to any study-specific pretreatment evaluations.

Study procedures assessments and their timing are described in the sections below and shown in the Time and Events Table ([Attachment 1](#)).

8.1. Efficacy

8.1.1. ***Efficacy Assessments at Baseline and during Study Treatment***

RECIST 1.1 ([Attachment 6](#)) will be applied as the primary measure for assessment of tumor response and date of disease progression. Local tumor imaging (investigator assessment with site radiological reading) will be used.

Tumor imaging should be performed by CT, which is preferred for the majority of patients, as the more commonly used modality. Magnetic resonance imaging (MRI) should only be used when CT is contraindicated or for imaging in the brain. The same imaging technique should be used for a patient throughout the trial. Imaging should include the chest, abdomen, and pelvis.

The subsections below describe in detail the tumor imaging and assessment measures at baseline and during study treatment (one or both study drugs, Section [4.1.3](#)).

8.1.1.1. **Baseline Tumor Imaging**

Initial tumor imaging at screening must be performed within 21 days prior to the date of enrollment (assignment to treatment) or within 28 days of the first dose of study treatment. The site study team must review screening images to confirm the patient has measurable disease per RECIST 1.1.

Scans performed as part of routine clinical management are acceptable for use as initial tumor imaging if they are of diagnostic quality and performed within protocol required time frame as described above.

8.1.1.2. **Tumor Imaging During Study Treatment**

During study treatment, tumor response will be assessed every 6 weeks (\pm 7 days) by investigator, with confirmatory assessment obtained at the next routine scheduled imaging time point (that is, after 6 weeks \pm 7 days). After 24 weeks, tumor assessment will be conducted every 12 weeks (\pm 7 days).

Per RECIST 1.1, partial or complete response should be confirmed by a repeat tumor imaging assessment not less than 4 weeks from the date the response was first documented. The tumor imaging for confirmation of response may be performed at the earliest 4 weeks after the first indication of response, or at the next scheduled scan (that is, 6 weeks \pm 7 days later), whichever is clinically indicated.

Continue to perform imaging until whichever of the following occurs first:

- disease progression confirmed by the second radiographic exam

- the start of new anticancer treatment
- withdrawal of consent
- death
- end of trial

